2.3 Exploratory Objectives

3 STUDY DESIGN

3.1 Overview of Study Design

This is an open-label, multinational, multicenter study to evaluate the long-term safety and tolerability of MEDI-546 in adult subjects with chronic, moderately-to-severely active SLE who were previously treated with investigational product (MEDI-546 or placebo) and completed Study CD-IA-MEDI-546-1013 through treatment and follow-up. The study will be conducted in approximately 240 subjects at up to 100 study sites.

Once subjects have completed treatment and follow-up in Study CD-IA-MEDI-546-1013 (through Day 422), signed the informed consent form (ICF), and met all study eligibility criteria, they may be enrolled in this OLE study. The start of this OLE study (defined as the day [Day 1] the subject receives their first dose of open-label MEDI-546) should occur within 28 days of the Day 422 visit of Study CD-IA-MEDI-546-1013 (with the exception of those subjects in the regions of Donetsk and Lugansk in the Ukraine, where the political situation necessitated a suspension of study activities) or at the discretion of the medical monitor if the start of this OLE study occurs outside the 28-day window. All subjects will receive IV MEDI-546 as a 300 mg fixed dose administered as an IV infusion over at least 30 minutes Q4W starting at Day 1 (Week 0) for up to 3 years or until the sponsor discontinues development of MEDI-546 for SLE, whichever comes first. All subjects will be followed for 85 days after receiving their last dose of MEDI-546.

At every visit, the investigator will evaluate the subject's clinical status and perform a risk/benefit analysis based on clinical judgment to determine if the subject should continue to receive MEDI-546 in the study.

Figure 3.1-1 Study Flow Diagram

IV = intravenous

The endpoints to be measured in this study are described in Section 7.3.

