4.2.1 Inclusion Criteria

Subjects must meet *all* of the following criteria:

- 1. Written informed consent and any locally required authorization (eg, HIPAA in the USA, EU Data Privacy Directive in the EU) obtained from the subject prior to performing any protocol-related procedures, including Day 1 evaluations.
- 2. Must have qualified for and received investigational product (MEDI-546 or placebo) and completed the treatment period plus the follow-up period (through Day 422) in Study CD-IA-MEDI-546-1013. Subjects who discontinued from Study CD-IA-MEDI-546-1013 are not eligible for this study, with the exception of those subjects in the regions of Donetsk and Lugansk in the Ukraine, where the political situation necessitated a suspension of study activities, and all other inclusion and exclusion criteria were met.
- 3. Females of childbearing potential who are sexually active with a nonsterilized male partner must use 2 methods of effective contraception for 28 days prior to Day 1, and must agree to continue using such precautions for 85 days after the final dose of investigational product; cessation of contraception after this point should be discussed with a responsible physician. Subjects must continue the use of their effective contraception as used in Study CD-IA-MEDI-546-1013. Periodic abstinence, the rhythm method, and the withdrawal method are not acceptable methods of contraception.
 - Females of childbearing potential are defined as those who are not surgically sterile (ie, bilateral tubal ligation, bilateral oophorectomy, or complete hysterectomy).
 - Postmenopausal is defined as 12 months with no menses without an alternative medical cause.

- Subjects must use 2 acceptable methods of effective contraception as described in Table 4.2.1-1.
- 4. Nonsterilized males who are sexually active with a female partner of childbearing potential must use 2 acceptable methods of effective contraception (see Table 4.2.1-1) from Day 1 for 85 days after receipt of the final dose of investigational product.

Table 4.2.1-1	Effective Methods of Contraception (Two Methods Must be
	Used)

	Barrier Methods		Intrauterine Device Methods		Hormonal Methods
•	Male condom plus	•	Copper T	•	Implants
	spermicide	•	Progesterone T ^a	•	Hormone shot or injection
•	Cap plus spermicide	•	Levonorgestrel-releasing	•	Combined pill
•	Diaphragm plus spermicide		intrauterine system (eg, Mirena [®]) ^a	•	Minipill
				•	Patch

^a This is also considered a hormonal method.

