4.2.2 Exclusion Criteria

Any of the following would exclude the subject from participation in the study:

General Exclusion Criteria

- 1. Any condition that, in the opinion of the investigator, would interfere with evaluation of the investigational product or interpretation of subject safety or study results.
- 2. Major surgery within 8 weeks before signing the ICF or elective major surgery planned during the study period (see Appendix 2 for guidance on major surgery).

Exclusion Criteria Related to Concomitant Medications:

- 3. Receipt of any of the following within the last 12 weeks:
 - Azathioprine > 200 mg/day.
 - Mycophenolate mofetil/mycophenolic acid > 2.0 g/day.
 - Oral, SC, or intramuscular methotrexate > 25 mg/week.

- 4. Receipt of any of the following:
 - Any live or attenuated vaccine within 4 weeks prior to signing the ICF (administration of killed vaccines is acceptable, the sponsor recommends investigators ensure all subjects are up to date on required vaccinations prior to study entry).
 - Bacillus of Calmette and Guerin (BCG) vaccine within 1 year of signing the ICF.

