4.2.3 Withdrawal Criteria

Permanent discontinuation of investigational product: An individual subject will not receive any further investigational product if any of the following occur in the subject in question:

- 1. Withdrawal of consent or lost to follow-up.
- 2. Adverse event (AE) that, in the opinion of the investigator or the sponsor, contraindicates further dosing with investigational product.
- 3. The investigator or the MedImmune medical monitor determines that withdrawal is in the subject's best interest.
- 4. Pregnancy, positive pregnancy test, or subject expresses an interest in becoming pregnant at any time from Day 1 through the active treatment period of the study (see Section 6.4.3.3).
- 5. Malignancy, except squamous or basal cell carcinoma of the skin with documented success of curative therapy.
- 6. An opportunistic or systemic fungal infection or any infection (viral, bacterial) of a serious nature (ie, requiring hospitalization or treatment with IV anti-infectives), that in the opinion of the investigator or medical monitor, contraindicates further dosing of investigational product after resolution.
- 7. Isolated hepatitis B core (HBc) positivity with hepatitis B virus (HBV) DNA detected by the central laboratory.
- Receipt of any of the following medications (other than MEDI-546 administered as per protocol) any time from the last MEDI-546 dose in Study CD-IA-MEDI-546-1013 to 85 days post last MEDI-546 dose in Study CD-IA-MEDI-546-1145:
 - Cyclophosphamide
 - IV corticosteroids > 1g Solu-Medrol or equivalent
 - IFN therapy (alpha 2a & 2b, beta 1a & 1b, and pegylated IFNs alpha 2a & 2b)
 - Investigational agents
 - Biologics (including belimumab)
 - Plasmapheresis
 - Any immunoglobulin (Ig) therapy
 - BCG vaccine

9. A diagnosis of active tuberculosis (TB), premature discontinuation of treatment for latent TB, or noncompliance with TB therapy

Subjects who are permanently discontinued from further receipt of investigational product, regardless of the reason (withdrawal of consent, due to an AE, other), will be identified as having permanently discontinued treatment. Subjects who permanently discontinue treatment may either be considered to have completed the study or not to have completed the study (see Section 4.7).

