4.6.2 Excluded Concomitant Medications

Subjects must be instructed not to take any medications, including over-the-counter products, without first consulting with the investigator.

The following medications are considered exclusionary if given from Day 1 to the end of the study.

- 1. Etanercept
- 2. Adalimumab, infliximab, or golimumab
- 3. Rituximab or certolizumab pegol
- 4. Azathioprine > 200 mg/day
- 5. Mycophenolate mofetil/mycophenolic acid > 2.0 g/day

- 6. Oral, SC, or intramuscular methotrexate > 25 mg/week
- 7. Any change in route of administration of oral, SC, or intramuscular methotrexate
- 8. Cyclophosphamide and leflunomide
- 9. IV corticosteroids
- 10. IFN therapy (alpha 2a & 2b, beta 1a & 1b, and pegylated IFNs alpha 2a & 2b)
- 11. Live or attenuated vaccines (the sponsor recommends that investigators ensure all subjects are up to date with required vaccinations prior to entry into the study)
- 12. Investigational agents
- 13. Biologics (including belimumab)
- 14. Plasmapheresis
- 15. Any Ig therapy
- 16. BCG vaccine

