5.1.2.1 Week 0; Day 1: First Infusion (Visit 1)

These procedures should be performed before using any of the Study CD-IA-MEDI-546-1013 data for this study:

- 1. Obtain written informed consent and appropriate privacy act document authorization (eg, HIPAA)
- 2. Assign an SID number

These procedures should be performed on the same day as investigational product administration on Day 1:

- 3. Verify eligibility criteria
- 4. Administer Short Form-36 Version 2 (SF-36v2; should be completed prior to any clinical assessments)
- 5. Review medical history and add any AEs/serious adverse events (SAEs)/AESIs (if appropriate)
- 6. Record concomitant medications (if appropriate)
- 7. Electrocardiogram (ECG; data to be used from Day 396 of Study CD-IA-MEDI-546-1013; required at Day 1 if not done at Day 396 of Study CD-IA-MEDI-546-1013)
- 8. Assess for Cushingoid features (if this assessment was performed on Day 365 of Study CD-IA-MEDI-546-1013, then data can also be used for Day 1 of this study)

If Day 1 of this study occurs on the same day as Day 422 (+ 28 days) of Study CD-IA-MEDI-546-1013, then the following procedures and samples can be collected one time and can be utilized for both studies; if Day 1 of this study does not occur on the same day as Day 422 (+ 28 days) of Study CD-IA-MEDI-546-1013, then the following procedures and samples should be collected at Day 1:

- 9. Perform physical examination (if applicable, record new findings as AEs or SAEs)
- 10. Measure weight
- 11. Collect **predose** blood samples
 - Serum chemistry
 - Hematology
 - Hepatitis B virus DNA polymerase chain reaction (PCR) TaqMan (subjects with isolated hepatitis B core antibody positivity during Study CD-IA-MEDI-546-1013 or at any time for the duration of this study will be tested monthly for HBV DNA. To remain eligible for this study, the subject's HBV DNA levels must remain undetectable as per the central lab [ie, < 29 IU/mL HBV DNA detected])
 - QuantiFERON-TB Gold (QFT-GIT; TB testing, only if negative or if indeterminate at any visit during Study CD-IA-MEDI-546-1013)
 - Immunology profile (antinuclear antibodies [ANA], extractable nuclear antigens [RNP, Sm, SSA, SSB], quantitative immunoglobulins)
 - Proteomics/biomarkers (optional)
 - Systemic Lupus Erythematosus Disease Activity Index-2000 (SLEDAI-2K)-associated lab tests (C3, C4, 50% hemolytic complement [CH50], anti-dsDNA)
 - Pharmacokinetics (MEDI-546 serum concentration)

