An AE includes but is not limited to any clinically significant worsening of a subject's pre-existing condition. An abnormal laboratory finding (including ECG finding) that requires an action or intervention by the investigator, or a finding judged by the investigator to represent a change beyond the range of normal physiologic fluctuation, should be reported as an AE. The worsening and/or flare of SLE disease activity will be captured in the disease activity assessments or other study-specific CRFs (ie, SLE Increase in Disease Activity CRF), and not recorded as an AE, unless it meets the definition for an SAE or AESI. If clinical sequelae are associated with a laboratory abnormality, the diagnosis or medical condition should be reported (eg, renal failure, hematuria) not the laboratory abnormality (eg, elevated creatinine, urine RBC increased). Abnormal laboratory values that are not, in the investigator's opinion, medically significant and do not require intervention should not be reported as AEs.

Adverse events may be treatment emergent (ie, occurring after initial receipt of investigational product) or nontreatment emergent. A nontreatment-emergent AE is any new sign or symptom, disease, or other untoward medical event that begins after written informed consent has been obtained but before the subject has received investigational product.

Elective treatment or surgery or preplanned treatment or surgery (that was scheduled prior to the subject being enrolled into the study) for a documented pre-existing condition that did not worsen from baseline is not considered an AE (serious or nonserious). An untoward medical event occurring during the prescheduled elective procedure or routinely scheduled treatment should be recorded as an AE or SAE.

Nonserious AEs will only be captured during the first year of subject's participation in the study; however, nonserious AEs that result in interruption of investigational product and/or discontinuation from the study will be captured at any time during the subject's participation in the study. Serious adverse events and AESIs will be captured throughout the entire study participation.

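### The 4-week live-vaccine look-back runs from consent and the on-study ban from Day 1, so no named rule covers the days between, except for BCG

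*Protocol*

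**What the plan says.** - **Look-back.** Protocol section 4.2.2, exclusion 4, first bullet: "Any live or attenuated vaccine within 4 weeks prior to signing the ICF". The same criterion accepts killed vaccines and advises that subjects be up to date on vaccinations before study entry.
- **On-study ban.** Section 4.6.2: "The following medications are considered exclusionary if given from Day 1 to the end of the study". Item 11 of that list begins "Live or attenuated vaccines (the sponsor recommends that investigators ensure all subjects are up to date". Section 4.5.5 makes Day 1 the first dosing day.
- **BCG.** Exclusion 4 gives it a separate one-year look-back. Withdrawal criterion 8 (section 4.2.3) also lists it, over a period that runs "any time from the last MEDI-546 dose in Study CD-IA-MEDI-546-1013 to 85 days post" the last dose of this study. No other live vaccine appears in that criterion, and Appendix 3 lists no vaccines.
- **Timing of Day 1.** Section 3.1 says it "should occur within 28 days of the Day 422 visit" of the parent study. The medical monitor may allow a later start, and subjects in Donetsk and Lugansk are exempt.
- **Consent and Day 1 as separate events.** Section 5.1.2.1 lists consent first and then opens a second group: "These procedures should be performed on the same day as investigational product administration on Day 1". Verification of eligibility is in that second group. Section 6.1.1 defines a nontreatment-emergent event as one that "begins after written informed consent has been obtained but before the subject has received investigational product".

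**The concern.** The likely reason for a 4-week look-back is to keep a live vaccine away from the first dose of an immunomodulator. The protocol gives no rationale, so this is an inference. The rule as written measures distance from a signature. The on-study ban does not pick up until the first infusion, so whenever consent comes earlier there is a stretch of days that neither rule reaches.

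Vaccination in that stretch is plausible. The protocol encourages sites to complete vaccinations before entry, and under section 4.3 a subject counts as enrolled only when the IVRS/IWRS assigns kit numbers, which is after consent. A site acting on that advice could give a live vaccine after consent and before Day 1 without breaking a named rule. Minimum separation would then rest on investigator judgment alone.

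**Working it through.** The plan states no figure to reproduce. The check sets the date windows against each other.

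**Convention.** Parent-study day numbers; C = day of consent; D = day of first infusion (Day 1 of this study). I read *within 4 weeks prior* as 1 to 28 days before the reference date. A vaccine given on the consent day itself is left unclassified, because the wording does not settle it.

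**Inputs.** Look-back of 28 days from C (section 4.2.2). Ban from D onward (section 4.6.2). D no later than 422 + 28 = 450 in the standard window (section 3.1). No maximum for D − C is stated.

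**Formulas, for live vaccines other than BCG.**
- Excluded before consent: days C − 28 to C − 1, which are D − C + 28 down to D − C + 1 days before infusion.
- Uncovered: days C + 1 to D − 1, a count of D − C − 1 (zero if C = D).
- Banned: D onward.

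**Results with D = 450.**

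| Consent day | Excluded vaccine days | Days before infusion | Uncovered days | Count | Shortest admitted separation |
|---|---|---|---|---|---|
| 422 | 394 to 421 | 56 to 29 | 423 to 449 | 450 − 422 − 1 = 27 | 450 − 449 = 1 day |
| 436 | 408 to 435 | 42 to 15 | 437 to 449 | 450 − 436 − 1 = 13 | 1 day |
| 450 | 422 to 449 | 28 to 1 | none | 0 | 29 days |

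In the first row the rule works backwards. A vaccine on Day 421 excludes the subject at 450 − 421 = 29 days before infusion, and one on Day 449 is admitted at 1 day.

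With the look-back anchored to Day 1, every consent date gives the third row. The shortest admitted separation is then 29 days, or 28 if a vaccine exactly 28 days earlier is held to fall outside the 4 weeks.

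**Does another rule fill the gap?**
- Withdrawal criterion 8 covers BCG throughout. Its entry for biologics cannot fairly be stretched to other live vaccines, because section 4.6.2 lists biologics, live vaccines and BCG as three separate items.
- Exclusion 1, withdrawal criterion 3 and the instruction in section 4.6.2 to consult the investigator before taking any medication are general. None names a vaccine or sets an interval.
- The parent study's vaccine rules are not in the documents. They could matter if consent came before Day 422. In the worked case the gap opens only after parent follow-up has ended.

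**The case against.** The strongest reply is that the planned path has no gap. Table 5.1-1 has no separate screening visit, consent sits in the Day 1 column, and the protocol provides for Day 1 to coincide with parent-study Day 422. The 27-day case is the edge of the standard window and should not be read as a typical value. This stands, and it limits how often the gap can matter. It does not remove the gap, because nothing requires same-day consent and sections 5.1.2.1 and 6.1.1 both allow for an interval.

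Second, several checks stand before the infusion. Section 3.1 asks for a risk/benefit judgment at every visit. On Day 1 eligibility is verified, medical history reviewed and concomitant medications recorded. An investigator would have to know of a vaccine given the day before and still choose to infuse. This makes the extreme case unlikely, but these checks supply no interval, and the eligibility check would apply the criterion as written.

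Third, dating from consent is common in this protocol: major surgery, BCG and the Appendix 3 washouts all use it. That explains the wording but does not repair it for live vaccines. For BCG, withdrawal criterion 8 bridges consent to Day 1. The protocol also has a Day 1 anchor next door in inclusion 3, under which the women it applies to "must use 2 methods of effective contraception for 28 days prior to Day 1".

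Finally, the analyses are descriptive, and no effect on an endpoint or analysis population has been shown. That is correct. The point concerns subject safety and the coherence of an entry rule.

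**Conclusion.** The gap is real and minor. For live or attenuated vaccines other than BCG, the written rules leave D − C − 1 whole days uncovered: none when consent and first infusion fall on the same date, and 27 when consent is at Day 422 and infusion at Day 450. The gap is longer if consent is signed before Day 422, if the medical monitor allows a later start, or under the Donetsk/Lugansk exemption. Whenever at least one whole day separates the two dates, the shortest separation that the named rules admit is 1 day.

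The wording gap follows directly from the text. Its practical effect depends on how often consent precedes Day 1, which the documents do not report, and on investigators not using their discretion. The safety argument also assumes that the look-back is meant to separate vaccine from dose.

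**What to change.** Change the first bullet of exclusion 4 so that the 4 weeks are counted back from Day 1, and check it at the eligibility step that section 5.1.2.1 already places on the infusion day. The 4-week length stays as it is.

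An alternative is to start item 11 of section 4.6.2 at ICF signing. This also closes the gap but is stricter than needed when consent is early. With consent at Day 422 and infusion at Day 450, everything from Day 394 onward would be barred, so the shortest admitted separation becomes 450 − 393 = 57 days. The Day 1 anchor is the cleaner choice.

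The cost is one phrase and an occasional postponed first infusion. A subject vaccinated the day before a planned infusion would wait about 4 weeks, which may need the medical monitor's agreement to start outside the 28-day window. Section 4.5.3 shows that some subjects had already been dosed when the current amendment was written, so the change helps only those still to be enrolled.

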4.2.3 Withdrawal Criteria

Permanent discontinuation of investigational product: An individual subject will not receive any further investigational product if any of the following occur in the subject in question:

- 1. Withdrawal of consent or lost to follow-up.
- 2. Adverse event (AE) that, in the opinion of the investigator or the sponsor, contraindicates further dosing with investigational product.
- 3. The investigator or the MedImmune medical monitor determines that withdrawal is in the subject's best interest.
- 4. Pregnancy, positive pregnancy test, or subject expresses an interest in becoming pregnant at any time from Day 1 through the active treatment period of the study (see Section 6.4.3.3).
- 5. Malignancy, except squamous or basal cell carcinoma of the skin with documented success of curative therapy.
- 6. An opportunistic or systemic fungal infection or any infection (viral, bacterial) of a serious nature (ie, requiring hospitalization or treatment with IV anti-infectives), that in the opinion of the investigator or medical monitor, contraindicates further dosing of investigational product after resolution.
- 7. Isolated hepatitis B core (HBc) positivity with hepatitis B virus (HBV) DNA detected by the central laboratory.
- Receipt of any of the following medications (other than MEDI-546 administered as per protocol) any time from the last MEDI-546 dose in Study CD-IA-MEDI-546-1013 to 85 days post last MEDI-546 dose in Study CD-IA-MEDI-546-1145:
 - Cyclophosphamide
 - IV corticosteroids > 1g Solu-Medrol or equivalent
 - IFN therapy (alpha 2a & 2b, beta 1a & 1b, and pegylated IFNs alpha 2a & 2b)
 - Investigational agents
 - Biologics (including belimumab)
 - Plasmapheresis
 - Any immunoglobulin (Ig) therapy
 - BCG vaccine

9. A diagnosis of active tuberculosis (TB), premature discontinuation of treatment for latent TB, or noncompliance with TB therapy

Subjects who are permanently discontinued from further receipt of investigational product, regardless of the reason (withdrawal of consent, due to an AE, other), will be identified as having permanently discontinued treatment. Subjects who permanently discontinue treatment may either be considered to have completed the study or not to have completed the study (see Section 4.7).

Subjects who are permanently discontinued from receiving investigational product will be followed for safety per Section 6.4, including the collection of any protocol-specified blood or urine specimens, unless consent is withdrawn or the subject is lost to follow-up or enrolled in another clinical study. Twenty-eight days (\pm 7 days) after the last dose of investigational product, subjects will begin the follow-up period by completing the Visit 41/Early Discontinuation Visit assessments. Two subsequent follow-up visits will also be completed 59 and 85 days (\pm 7 days) after the last dose of investigational product as per the schedule of study procedures. A subject who receives any SLE medication or SLE treatment listed in Appendix 3 (other than those prohibited medications or treatments listed above) may be allowed to continue receiving investigational product only if permission from the sponsor is obtained.

Concomitant medications that require the sponsor to be notified immediately and the medical monitor to be consulted to determine if a subject may continue to receive investigational product include, but are not limited to:

- Corticosteroids with a long biologic half-life (eg, dexamethasone, betamethasone)
- Increase in oral corticosteroids (OCS) treatment above a total dose > 40 mg/day for a dosing period > 14 days, dosing with MEDI-546 may be continued, unless there is a safety concern. However, it should be noted that frequent steroid use above Study CD-IA-MEDI-546-1013 baseline for SLE disease control (> 2 times every 6 months, higher doses [> 40 mg/day], and/or longer duration than permitted by the protocol) after 12 months of open-label MEDI-546 should result in discontinuation of MEDI-546 administration for failure to achieve a favorable benefit:risk profile.

Withdrawal of consent: If consent is withdrawn, the subject will not receive any further investigational product or further study observation. Note that the subject may need to undergo additional tests or tapering of treatment to withdraw safely.

Lost to follow-up: Subjects will be considered lost to follow-up only if no contact has been established by the time the study is completed (as defined in Section 4.9) such that there is insufficient information to determine the subjects' status as of their last visit.

• Note: Subjects refusing to return to the site or to continue participation in the study should be documented as "withdrawal of consent" rather than "lost to follow-up." Investigators should document attempts to re-establish contact with missing subjects throughout the study period. If contact with a missing subject is re-established, the subject should not be considered lost to follow-up and any evaluations should resume according to the protocol.

